5. STUDY OUTCOMES

5.1 Primary Outcome

The primary outcome will be the continuous smoking abstinence from target quit date to the 6-month follow-up visit, ascertained by self-report (self-report of no smoking from target quit date) and confirmed by exhaled CO level (CO<10 ppm) and urinary level of cotinine and anabasine (<3 ng/ml) and NNAL (10 pg/mg creat).[1, 33, 34]

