

Outcome(s):
	
Primary outcome
 
 - The primary outcome at 6 month will be the continuous smoking abstinence from target quit date to the 6-month follow-up visit, ascertained by self-report (self-report of no smoking from target quit date) and confirmed by urinary levels of anabasine (<3 ng/ml). - The primary outcome at 12- and 24- months will be the self-reported 7-day point prevalence abstinence (not having smoked cigarettes within the preceding week), confirmed by urinary levels of anabasine (<3 ng/ml). 
Secondary outcomes
 
 - Secondary smoking cessation outcome will alternate definitions of the smoking cessation outcome: as the primary outcome, but allowing up to 5 cigarettes in total and a 2-week 'grace period' after the target quit date, self-reported 7-day point prevalence abstinence, all confirmed by urinary level of anabasine. We will also apply alternate definitions of the validation of exposure to tobacco smoking with: exhaled CO levels (CO<10 ppm) and NNAL (<10 pg/ml creat) and exposure to nicotine (from tobacco cigarettes, ENDS or NRTs) with urinary levels of cotinine. We will further report on change in the self-reported number of cigarettes smoked per day (CPD), with 50% reduction in CPD from baseline to follow-up considered as successful reduction. - Concentrations of urinary tobacco-specific nitrosamines (TSNAs), volatile organic compounds (VOCs), aldehydes and polycyclic aromatic hydrocarbons (PAHs) for all participants. Participants will complete a detailed questionnaire to account for other sources of exposure to these chemicals. - Respiratory symptoms (self-report) - Oxidative stress assessed by 8-OHdG and 8-isoprostane concentrations in both exhaled breath condensate (EBC) and urine; - Cardiovascular risk factors (CVRF) assessed by HDL- and LDL-cholesterol, HbA1c, creatinine, blood pressure levels, waist circumference, and body mass index. - Adverse events (AEs), serious adverse events (SAEs) following international standards. - Mood, anxiety and sleep quality (Self report) - Pulmonary function, measured by conventional pulmonary function tests and by multiple breath washout (MBW). - Structural and functional outcomes as ventilation and perfusion of the lung, measured by MRI. - Micronuclei (MN) in buccal epithelium - Olfactory function assessed by the Burghart Sniffin' Sticks (odor identification score (OIS)). - Dry-hit recognition - Detection of inflammatory biomarkers

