5.2 Secondary Outcomes

The secondary outcomes are as follows:

- Secondary smoking cessation outcomes:

6 month follow-up:

- Continuous smoking abstinence. Self-report of having smoked no cigarettes from TQD, validated by urinary levels of NNAL (4-(methylnitrosamino)-1-(3-pyridyl)-1-butanol). If NNAL is missing, validation by urinary levels of anabasine or exhaled CO.
- Self-reported smoking abstinence allowing a 2-week 'grace period' after the TQD
- Validated smoking abstinence allowing a 2-week 'grace period' after the TQD, validated by urinary levels of anabasine. If anabasine is missing validation by exhaled CO.
- Validated smoking abstinence allowing a 2-week 'grace period' after the TQD, validated by urinary levels of NNAL. If NNAL is missing, validation by urinary levels of anabasine or exhaled CO.
- Self-reported smoking abstinence allowing up to 5 cigarettes in total after the TQD.
- Validated smoking abstinence allowing up to 5 cigarettes in total after the TQD, validated by urinary levels of anabasine. If anabasine is missing validation by exhaled CO.
- Validated smoking abstinence allowing up to 5 cigarettes in total after the TQD, validated by urinary levels of NNAL. If NNAL is missing, validation by urinary levels of anabasine or exhaled carbon monoxide (CO).
- Self-reported 7-day point prevalence abstinence at 6 months, Self-report of having smoked no cigarettes in the past seven days.
- Validated 7-day point prevalence abstinence. Confirmation of having smoked no cigarettes in the past seven days, validated by urinary levels of anabasine. If anabasine is missing validation by exhaled carbon monoxide (CO).
- Validated 7-day point prevalence abstinence. Confirmation of having smoked no cigarettes in the past seven days, validated by urinary levels of NNAL. If NNAL is missing, validation by urinary levels of anabasine or exhaled carbon monoxide (CO).
- Number of cigarettes smoked per day (CPD), self-reported, at baseline, TQD, phone visits and 6 months visit
- Change in number of cigarettes smoked per day (CPD), self-reported. Successful reduction defined as 50% reduction in CPD.
- Concentrations of urinary TSNAs (NNN, NNK and its metabolite NNAL), VOCs and PAHs (1- and 2-Naphtol and 1-OHP)
- Respiratory symptoms assessed by questionnaire (CAT, mMRC, ACT, ECRHS) ¹³⁴⁻¹³⁷
- Oxidative stress assessed by 8-OHdG and 8-isoprostane concentrations in both EBC and urine

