2.8 Blinding

Participants, nurses and investigators will not be blinded. The laboratory personnel will be blinded for the determination of all urinary metabolites of nicotine (anabasine, cotinine, nornicotine, 3-OH cotinine). Any adverse event occurred in this study that generated care by a physician will be verified by a blinded external committee whenever possible. ~~The statistician who authors this SAP and performs the blinded~~

CTU Bern	SAP for: ESTxENDS	Version: 1-02.0
----------	-------------------	---------------------------------

CTU Bern	Template: Statistical Analysis Plan (SAP)	Version: 03	
	Code: CS_STA_TEM-11	Valid from: 28-02-2019 5.6.2023	Page 7 of 27

~~primary ITT and secondary per-protocol analysis of the primary and secondary smoking cessation outcomes will be blinded.~~ All ~~other~~ statisticians and data managers will not be blinded. The laboratory personnel will not be blinded for further urinary measures of exposures such as metabolites of polycyclic aromatic hydrocarbons (PAHs), of VOCs, creatinine and metabolites of TSNAs (NNAL, NNN, NNK).

There will be an automatic import of these urinary lab values into the database, programmed by a CTU data manager. Specific procedure and time points will be defined.

~~Breaking the blind:~~

~~The blinded statistician will be unblinded when all outcomes with blinding of the primary analysis are completely analysed. An unblinded statistician will have to download and label the data and prepare the analysis sets for the blinded analysis.~~

CTU Bern	SAP for: ESTxENDS	Version: 1.02.0	
CTU Bern	Template: Statistical Analysis Plan (SAP)	Version: 03	
	Code: CS_STA_TEM-11	Valid from: 28.02.2019 5.6.2023	Page 8 of 27

3. Data management

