6.2 Derivation of Outcomes

Comments to secondary smoking cessation outcomes:

- Smoking is allowed during the grace period.
- The number of cigarettes smoked since the last visit is recorded as a categorical variable (1-5 cigarettes, >5 cigarettes). If the participant smoked more than once a day cigarettes in the last 7 days, the value is recorded as numeric variable. For secondary smoking cessation outcomes, we will assume the median value for the categorical variable. I.e. if a subject records 2 times to smoke 1-5 cigarettes, we assume him to be over the limit of 5 cigarettes.

Table 3: Derivation of primary and secondary outcomes.

Outcome	eCRF sheet	Variable	Variable type	Derivation	Outcome type
Primary: continuous smoking abstinence from target quit date to the 6-month follow-up visit AND	cig_ecig	quit_smoke_again	Binary: No, Yes	{ [Week 1/2/4/8, and month 6] quit_smoke_again == No AND quit_tobacco_inhale ==	Binary
		quit_tobacco_inhale	Binary: No, Yes		
	cig_ecig_6m	quit_smoke_again	Binary: No, Yes		
		quit_tobacco_inhale	Binary: No, Yes		

CTU Bern	SAP for: ESTxENDS	Version: 1-02.0
-----------------	-------------------	---------------------------------

CTU Bern	Template: Statistical Analysis Plan (SAP)	Version: 03
	Code: CS_STA_TEM-11	Valid from: 28-02-2019 to 05-06-2023

urinary level of anabasine (<3 ng/ml) OR	to be defined	to be defined	to be defined	No} AND {x < 3 if x!=missing, vs_co2_level<10 if x==missing & vs_co2_level ==missing}
CO level	vital_6m	vs_co2_level	Continuous	
Secondary outcomes				
continuous smoking abstinence from target quit date to the 6-month follow-up visit AND	Cig_ecig, cig_ecig_6m	quit_smoke_again, quit_tobacco_inhale	Binary: No, Yes, Binary:No, Yes	{[Week 1/2/4/8, and month 6] quit_smoke_again == No AND quit_tobacco_inhale == No} AND
urinary level of NNAL (<10 pg/ml creat) OR	To be defined	To be defined	To be defined	{y < 10 if y!=missing, x<3 if y==missing & x!=missing, vs_co2_level<10 if y==missing & x==miss- ing & vs_co2_level!=missing }
urinary level of anabasine (<3 ng/ml) OR	To be defined	To be defined	To be defined	
CO level	Vital, Vital_6m	vs_co2_level	continuous	
Continuous smoke abstinence allowing a 2-week grace period after TQD	cig_ecig / cig_ecig_6m	quit_smoke_again quit_tobacco_inhale	Binary: No, Yes	[Week 4, Week 8, and 6 months] sum(quit_smoke_again == No) >= 2 AND sum(quit_tobacco_in- hale == No) >= 2

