Cholesterin (total)	vital vital_6m	lab_choles_total	continuous (mmol/L)	lab_choles_total[vital_6m] – lab_choles_total[vital]	continuous (mmol/L)
LDL cholesterol	calculated	calculated	Continuous (mmol/L)	lab_choles_total[vital_6m]-lab_choles_hdl[vital_6m]- (lab_triglyceride[vital_6m] /5)-lab_choles_total[vital]-lab_choles_hdl[vital]- (lab_triglyceride[vital] /5) [Friedewald formula]	continuous (mmol/L)
HDL cholesterol	vital vital_6m	lab_choles_hdl	continuous (mmol/L)	lab_choles_hdl[vital_6m] – lab_choles_hdl[vital]	continuous (mmol/L)
triglycerides	vital vital_6m	lab_triglyceride	continuous (mmol/L)	lab_triglyceride[vital_6m] - lab_triglyceride[vital]	continuous (mmol/L)
blood pressure	vital vital_6m	vs_bpressure_sys1-3, vs_bpressure_dias1-3	continuous (mmHg)	mean(vs_bpressure_sys1-3), mean(vs_bpressure_dias1-3)	continuous (mmHg)
heart rate (mean of the second and third measure)	vital vital_6m	vs_heart_rate_2 vs_heart_rate_3	continuous (bpm)	mean(vs_heart_rate_2, vs_heart_rate_3)[vital_6m] – mean(vs_heart_rate_2, vs_heart_rate_3)[vital]	continuous (bpm)
waist circumference	vital vital_6m	vs_waist_cm	continuous (cm)	vs_waist_cm[vital_6m] - vs_waist_cm[vital]	continuous (cm)
BMI	vital vital_6m	bmi	continuous (kg/m ²)	bmi[vital_6m] – bmi[vital]	continuous (kg/m ²)
Lab values					
Metabolites of nicotine:					

CTU Bern	SAP for: ESTxENDS	Version: 4.02.0
----------	-------------------	---------------------------------

CTU Bern	Template: Statistical Analysis Plan (SAP)	Version: 03	
	Code: CS_STA_TEM-11	Valid from: 28.02.2019 5.6.2023	Page 22 of 27

Anabasine	To be defined	To be defined	dichotomized at <3 ng/ml	anabasine < 3	Binary: <3ng/ml, ≥3ng/ml
Metabolites of TSNAs:					
NNAL	To be defined	To be defined	dichotomized at <10pg/ml	NNAL < 10	Binary: <10pg/ml, ≥10pg/ml

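### The NNAL cut-off for four secondary 6-month cessation outcomes is not in a valid unit and conflicts with the limit given elsewhere in the same SAP table

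*Supplement*

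**What the plan says.** Four secondary outcomes in SAP 2.0, section 6.2, Table 3 are confirmed by urinary NNAL at 6 months: continuous abstinence, abstinence with the two-week grace period, abstinence allowing up to five cigarettes, and 7-day point prevalence. Each of the four rows gives the limit as "urinary level of NNAL (<10 pg/ml creat) OR". The derivation column contains "y < 10 if y!=missing", and the form, variable and variable type for NNAL are left open. Anabasine is consulted only when NNAL is missing, and CO only when both are missing.

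At the end of the same table, the Lab values row has NNAL "dichotomized at <10pg/ml". Both resulting categories are in pg/ml, without creatinine.

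The latest protocol does not settle the matter. The synopsis of protocol 9.0 lists the alternative validation limits as "exhaled CO levels (CO<10 ppm) and NNAL (<10 pg/ml creat". Section 5.2 says only that continuous abstinence is "validated by urinary levels of NNAL (4-(methylnitrosamino)-1-(3-pyridyl)-1-butanol" and gives no number or unit. SAP section 6.1 gives none for NNAL either.

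Urinary creatinine is available: SAP 2.0, section 2.8 names "creatinine and metabolites of TSNAs (NNAL, NNN, NNK" among the urinary laboratory measures. The superseded protocol 2.0, section 5.1, had "NNAL (10 pg/mg creat", which is a proper creatinine-corrected unit.

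**The concern.** A cut-off that turns a laboratory value into abstinent or smoking has to be on one defined scale. Here the outcome rows point to a creatinine correction through the word creat, the denominator ml points to urine volume, and the Lab values row states urine volume outright. Two programmers could both follow Table 3, one using NNAL as measured and the other dividing it by creatinine, and produce different outcome variables.

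NNAL takes precedence over anabasine and CO in these four outcomes. The scale therefore decides validation for every self-reported abstainer who has an NNAL value. The outcomes also serve as an alternative biochemical check on the anabasine-based results, and that check is weaker if its threshold is undefined. SAP 2.0 makes all analyses unblinded, and its section 2.8 says laboratory staff are not blinded for NNAL or creatinine. The scale is better settled in writing than left to whoever codes the variable.

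**Working it through.** No sample-size, power or alpha figure is involved, so there is no figure of the plan's own to reproduce. The check is a comparison of texts followed by a unit conversion.

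**1. Texts side by side (latest versions).**

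| Place | NNAL limit |
|---|---|
| SAP 2.0 Table 3, four outcome rows | 10, in pg/ml creat |
| SAP 2.0 Table 3, derivation code | y below 10, no unit, y not defined |
| SAP 2.0 Table 3, Lab values row | 10 pg/ml |
| Protocol 9.0 synopsis | 10, in pg/ml creat |
| Protocol 9.0 section 5.2; SAP 2.0 section 6.1 | none stated |

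The faulty unit recurs identically in the synopsis prose and in four table rows, so it is not an artefact of text extraction.

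**2. Conversion.** NNAL [pg/mg creatinine] = NNAL [pg/ml] ÷ urinary creatinine [mg/ml]. A limit of 10 pg/mg creatinine therefore equals 10 × creatinine in pg/ml, and coincides with 10 pg/ml only at a creatinine of 1 mg/ml.

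**3. Size of the gap.** The documents give no creatinine values, so the range below is an assumption.

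| Creatinine (mg/ml) | 10 pg/mg expressed in pg/ml | NNAL values classified differently (pg/ml) |
|---|---|---|
| 0.3 | 3 | 3 to under 10 |
| 0.5 | 5 | 5 to under 10 |
| 1.0 | 10 | none |
| 1.5 | 15 | 10 to under 15 |
| 2.0 | 20 | 10 to under 20 |
| 3.0 | 30 | 10 to under 30 |

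**4. Illustrations (assumed values).**
- NNAL 7 pg/ml, creatinine 0.5 mg/ml: 7 is below 10, so abstinent on the volume scale; 7 ÷ 0.5 = 14 pg/mg, so smoking on the corrected scale.
- NNAL 15 pg/ml, creatinine 2.0 mg/ml: 15 is above 10, so smoking on the volume scale; 15 ÷ 2.0 = 7.5 pg/mg, so abstinent on the corrected scale.

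Reclassification can go either way. The number of participants affected cannot be derived, because the documents give no joint distribution of NNAL and creatinine.

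**The case against.** The strongest reply is that this is a one-letter slip, ml for mg. The four outcome rows agree with each other and with the synopsis, all keep creat, creatinine is measured, and the urinary biomarkers in protocol Table 11.2-2 are all expressed per unit of creatinine. The Lab values row stands apart, and NNAL as a stand-alone dichotomy is not among the outcomes listed in SAP section 6.1. This makes pg/mg creatinine the likelier intention. It does not remove the contradiction within Table 3, and no current text states pg/mg.

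Several limits stand:

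- **Reach.** Only secondary validation variants are touched. Each has an anabasine-validated counterpart; for continuous abstinence that counterpart is the primary outcome.
- **Condition.** NNAL matters only for participants who pass the self-report condition and have an NNAL value.
- **Undefined variables.** The form and variable for anabasine are equally left open in Table 3, so the open fields alone are not the fault. The fault is an undefined y together with conflicting units.

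A reader might infer more than the documents support:

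- **That volume-scale validation is wrong because dilute urine passes it.** The primary outcome's anabasine limit of 3 ng/ml is also uncorrected, so this argument does not single out NNAL or show which scale was meant.
- **That all the 12- and 24-month NNAL outcomes carry the same error.** SAP 2.0 excludes those visits, and protocol section 5.2 names NNAL validation there without a cut-off. They are affected only in so far as they take their limit from the synopsis.
- **That the treatment comparison is biased.** The same rule applies to both arms, and no direction can be shown.

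**Conclusion.** The point holds as an error in a decision threshold for secondary outcomes. The NNAL limit in four rows of SAP 2.0 Table 3 and in the protocol 9.0 synopsis is not in a valid unit, it conflicts with the Lab values row of the same table, and nothing in the latest protocol or SAP resolves it. It should be corrected, but it does not threaten the primary result.

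The conclusion that the two readings can disagree rests on reading creat as a correction per mg of creatinine, which is the natural reading and matches the superseded protocol. The size, a limit anywhere from 3 to 30 pg/ml in place of 10, rests on the assumed creatinine range of 0.3 to 3 mg/ml. The documents do not allow any statement about the change in quit rates or relative risk.

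**What to change.** Choose one NNAL unit before the NNAL outcomes are derived. If they have already been derived, document which scale was used. State the same unit in the four outcome rows, the Lab values row and the protocol synopsis, and define y explicitly.

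The creatinine-corrected form is the better candidate: NNAL below 10 pg/mg creatinine, with y = urinary NNAL in pg/ml divided by urinary creatinine in mg/ml. It fits the word creat, and it is the only coherent creatinine-corrected NNAL unit that the documents give. Since it comes from superseded text, the sponsor should confirm it. If the volume scale was intended, delete creat throughout and say that y is uncorrected. Classification on the other scale can be reported as a sensitivity analysis. The limit that applies to the 12- and 24-month NNAL outcomes should be stated at the same time.

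The cost is a few words in the SAP and the synopsis and at most one division in the code. The laboratory already measures creatinine, so no new data are needed.

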6.1 Outcome definitions

Primary outcome: The primary outcome will be the continuous cigarette smoking abstinence from target quit date to the 6-month follow-up visit, ascertained by self-report at the 6-month follow-up exam (self-report of no smoking from target quit date) and confirmed by urinary level of anabasine (<3 ng/ml). If anabasine is missing, validation by exhaled carbon monoxide (CO). The outcome is a binary outcome.

Core secondary outcomes:

- Secondary smoking cessation outcomes to the 6-month follow-up visit:
 - Continuous smoking abstinence. Self-report of having smoked no cigarettes from TQD, validated by urinary levels of NNAL (4-(methylnitrosamino)-1-(3-pyridyl)-1-butanol). If NNAL is missing, validation by urinary levels of anabasine or exhaled CO.
 - Self-reported smoking abstinence allowing a 2-week 'grace period' after the TQD
 - Validated smoking abstinence allowing a 2-week 'grace period' after the TQD, validated by urinary levels of anabasine. If anabasine is missing validation by exhaled CO.
 - Validated smoking abstinence allowing a 2-week 'grace period' after the TQD, validated by urinary levels of NNAL. If NNAL is missing, validation by urinary levels of anabasine or exhaled CO.
 - Self-reported smoking abstinence allowing up to 5 cigarettes in total after the TQD.
 - Validated smoking abstinence allowing up to 5 cigarettes in total after the TQD, validated by urinary levels of anabasine. If anabasine is missing validation by exhaled CO.
 - Validated smoking abstinence allowing up to 5 cigarettes in total after the TQD, validated by urinary levels of NNAL. If NNAL is missing, validation by urinary levels of anabasine or exhaled carbon monoxide (CO).
 - Self-reported 7-day point prevalence abstinence at 6 months, Self-report of having smoked no cigarettes in the past seven days.
 - Validated 7-day point prevalence abstinence. Confirmation of having smoked no cigarettes in the past seven days, validated by urinary levels of anabasine. If anabasine is missing validation by exhaled carbon monoxide (CO).
 - Validated 7-day point prevalence abstinence. Confirmation of having smoked no cigarettes in the past seven days, validated by urinary levels of NNAL. If NNAL is missing, validation by urinary levels of anabasine or exhaled carbon monoxide (CO).

CTU Bern	SAP for: ESTxENDS	Version: 4.02.0	
CTU Bern	Template: Statistical Analysis Plan (SAP)	Version: 03	
	Code: CS_STA_TEM-11	Valid from: 28.02.2019 to 06.2023	Page 18 of 27

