Continuous smoke abstinence allowing a 2-week grace period after TQD AND	cig_ecig / cig_ecig_6m to be defined	quit_smoke_again quit_tobacco_inhale quit_smoke_n	Binary: No, Yes Binary: No, Yes categorical: 1-5 cigarettes, > 5 cigarettes	{[Week 4, Week 8, and 6 months] sum(quit_smoke_again == No) >= 2 AND sum(quit_tobacco_in- hale == No) >= 2 AND sum(quit_smoke_n == 1-5) <= 1} AND { x < 3 if x!=missing, vs_co2_level<10 if x==missing & vs_co2_level ==missing}
urinary level of anabasine (<3 ng/ml) OR	To be defined	To be defined	To be defined	
CO level	Vital, Vital_6m	vs_co2_level	continuous	
Continuous smoke abstinence allowing a 2-week grace period after TQD AND	cig_ecig / cig_ecig_6m to be defined	quit_smoke_again quit_tobacco_inhale quit_smoke_n	Binary: No, Yes Binary: No, Yes categorical: 1-5 cigarettes, > 5 cigarettes	{[Week 4, Week 8, and 6 months] sum(quit_smoke_again == No) >= 2 AND sum(quit_tobacco_in- hale == No) >= 2 AND sum(quit_smoke_n == 1-5) <= 1} AND { y < 10 if y!=missing, x<3 if y==missing & x!=missing, vs_co2_level<10 if
urinary level of NNAL (<10 pg/ml creat) OR	To be defined	To be defined	To be defined	
urinary level of anabasine (<3 ng/ml) OR	To be defined	To be defined	To be defined	

CTU Bern	SAP for: ESTxENDS	Version: 1.02.0
----------	-------------------	---------------------------------

CTU Bern	Template: Statistical Analysis Plan (SAP)	Version: 03
	Code: CS_STA_TEM-11	Valid from: 28.02.2019 to 05.06.2023

CO level	Vital, Vital_6m	vs_co2_level	continuous	y==missing & x==missing & vs_co2_level!=missing }	
Self-reported smoking abstinence allowing up to 5 cigarettes in total after the TQD	cig_ecig / cig_ecig_6m	quit_smoke_n	categorical	sum(quit_smoke_n == 1-5) <= 1	Binary
Self-reported smoking abstinence allowing up to 5 cigarettes in total after the TQD AND	cig_ecig / cig_ecig_6m	quit_smoke_n	Categorical	sum(quit_smoke_n == 1-5) <= 1 AND	Binary
urinary level of anabasine (<3 ng/ml) OR	To be defined	To be defined	To be defined	{ x < 3 if x!=missing, vs_co2_level<10 if x==missing & vs_co2_level ==missing}	
CO level	Vital, Vital_6m	vs_co2_level	continuous		
Self-reported smoking abstinence allowing up to 5 cigarettes in total after the TQD AND	cig_ecig / cig_ecig_6m	quit_smoke_n	Categorical	sum(quit_smoke_n == 1-5) <= 1 AND	Binary

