urinary level of NNAL (<10 pg/ml creat) OR	To be defined	To be defined	To be defined	{ y < 10 if y!=missing, x<3 if y==missing & x!=missing, vs_co2_level<10 if y==missing & x==missing & vs_co2_level!=missing }	
urinary level of anabasine (<3 ng/ml) OR	To be defined	To be defined	To be defined		
CO level	Vital, Vital_6m	vs_co2_level	continuous		
Self-reported 7-day point prevalence abstinence at 6 months	cig_ecig_6m	quit_smoke_again, quit_smoke_7days	Binary: No, Yes	quit_smoke_again == No AND quit_smoke_7days == No	Binary
Self-reported 7-day point prevalence abstinence at 6 months AND	cig_ecig_6m	quit_smoke_again, quit_smoke_7days	Binary: No, Yes Binary: No, Yes	{ quit_smoke_again == No AND quit_smoke_7days == No} AND { x < 3 if x!=missing, vs_co2_level<10 if x==missing & vs_co2_level ==missing}	Binary
urinary level of anabasine (<3 ng/ml) OR	To be defined	To be defined	To be defined		
CO level	Vital, Vital_6m	vs_co2_level	continuous		
Self-reported 7-day point prevalence abstinence AND	cig_ecig_6m	quit_smoke_again, quit_smoke_7days	Binary: No, Yes	{quit_smoke_again == No AND quit_smoke_7days == No} AND	Binary
urinary level of NNAL (<10 pg/ml creat) OR	To be defined	To be defined	To be defined	{y < 10 if y!=missing, x<3 if y==missing & x!=missing, vs_co2_level<10 if	
urinary level of anabasine (<3 ng/ml) OR	To be defined	To be defined	To be defined		

CTU Bern	SAP for: ESTxENDS	Version: 4.02.0
----------	-------------------	---------------------------------

CTU Bern	Template: Statistical Analysis Plan (SAP)	Version: 03
	Code: CS_STA_TEM-11	Valid from: 28.02.2019 5.6.2023

CO level	Vital, Vital_6m	vs_co2_level	continuous	y==missing & x==missing & vs_co2_level!=missing}	
Number of cigarettes smoked per day (CPD)	cig_ecig / cig_ecig_6m	quit_more1perday	continuous (number of cigarettes per day in the last 7 days)	[BL, TQD, phone visits and 6-month visit] quit_more1perday	Continuous
Change in the self-reported number of cigarettes smoked per day in the last 7 days	cig_ecig / cig_ecig_6m	quit_more1perday	continuous (number of cigarettes per day in the last 7 days)	(quit_more1perday[month 6] / quit_more1perday[day 0]) >= 0.5 IF [month 6]{contact_estab_yn == Yes AND quit_smoke_again == Yes AND quit_smoke_7days == Yes AND quit_smoke_nperday == ">=1x/Tag"} ELSE TRUE	Binary
CAT	cat / cat_6m	q1 to q8	radio (0 to 5)	sum(q1 to q8)[cat_6m] – sum(q1 to q8)[cat]	continuous (score scale 0-40, difference can be 0-40 as well)

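### SAP 2.0 Table 3 derives three families of secondary cessation outcomes in ways that contradict their definitions, and gives the NNAL cut-off in two units

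*Supplement*

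**What the plan says.** SAP 2.0 section 6.1 lists ten secondary abstinence outcomes. Nine of them form three families, each with a self-report version, an anabasine-validated version and an NNAL-validated version:

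- **Up to 5 cigarettes:** "Self-reported smoking abstinence allowing up to 5 cigarettes in total after the TQD".
- **Grace period:** abstinence to month 6, with smoking tolerated only in the first two weeks after the TQD.
- **7-day point prevalence:** "Self-report of having smoked no cigarettes in the past seven days".

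The comments at the start of section 6.2 describe the data. "The number of cigarettes smoked since the last visit is recorded as a categorical variable (1-5 cigarettes, >5 cigarettes"). Participants smoking more than once a day in the last 7 days have a numeric value recorded instead. A '1-5' answer is taken at its median, so two such answers put a participant over the limit.

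Table 3 then gives the derivations:

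- All three up-to-5 rows: "sum(quit_smoke_n == 1-5) <= 1".
- Grace-period rows: "Week 4, Week 8, and 6 months] sum(quit_smoke_again == No) >= 2", with the same count for `quit_tobacco_inhale`. The two validated rows also carry the up-to-5 condition on `quit_smoke_n`; the self-report row does not.
- 7-day rows: "quit_smoke_again == No AND quit_smoke_7days == No".
- NNAL: "urinary level of NNAL (<10 pg/ml creat") in the validation rows, but "dichotomized at <10pg/ml" in the laboratory rows.

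Section 6.3.1 has all of these analysed in the same way as the primary outcome.

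**The concern.** Table 3 is the part of the SAP a programmer will code from. In each family the coded rule and the written definition classify some participants differently. In the up-to-5 family the coded rule even reverses the order: two '1-5' answers fail, while five '>5' answers pass.

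The results at stake are reported proportions, relative risks and risk differences for core secondary outcomes. A rule that labels continuing smokers abstinent inflates the rate in both arms and can distort the contrast in either direction. The 7-day measure at month 6 would also differ by definition from the 7-day primary outcome that protocol 9.0 (section 5.1) sets for 12 and 24 months.

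**Working it through.** This is a check of logic. The inputs are the definitions in 6.1, the comments in 6.2 and the expressions in Table 3.

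**1. Up to 5 cigarettes.** First, the SAP's own text rule: the median of 1 to 5 is 3, and 2 × 3 = 6 > 5, so two '1-5' answers exceed the limit. This reproduces.

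The up-to-5 rows list no visits, so I take the five contacts used for the primary outcome (weeks 1, 2, 4, 8 and month 6). With three answers each (none, '1-5', '>5') there are 3^5 = 243 patterns.

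- Text rule ('1-5' counts as 3, '>5' as at least 6, total at most 5): no smoking at any contact, or exactly one '1-5' and otherwise none. That is 1 + 5 = 6 patterns.
- Table 3 rule (at most one '1-5', no condition on '>5'): 2^5 + 5 × 2^4 = 32 + 80 = 112 patterns.
- Difference: 112 − 6 = 106 patterns, each with at least one '>5' answer. With '>5' five times, the count of '1-5' is 0, and 0 ≤ 1 passes.
- Adding the condition that no answer is '>5' brings the count back to 6, identical to the text rule.

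A daily smoker with only the numeric value may have no `quit_smoke_n` entry. That also gives a count of 0 and passes.

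**2. Grace period.** There are 2^3 = 8 answer patterns over week 4, week 8 and month 6.

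| Week 4 / Week 8 / Month 6 (smoked?) | Table 3 | Definition |
|---|---|---|
| No / No / No | abstinent | abstinent |
| No / No / Yes | abstinent | not |
| No / Yes / No | abstinent | not |
| Yes / No / No | abstinent | not |
| the other four | not | not |

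Table 3 passes 4 of 8 patterns; the definition passes 1 of 8. In the validated rows the extra `quit_smoke_n` limit does not close the gap. No / No / Yes with '>5' at month 6 still satisfies both conditions.

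**3. 7-day point prevalence.** There are 2^2 = 4 patterns of `quit_smoke_again` and `quit_smoke_7days`. The definition needs only the second to be 'No', so 2 of 4 pass. Table 3 needs both, so 1 of 4 passes. The pattern lost is smoked again, but not in the last 7 days. If `quit_smoke_again` covers the time since the previous contact, that is roughly day 56 to day 180, or 124 days, rather than 7. This recall period is inferred from how the primary outcome is assembled contact by contact; the SAP does not print the item.

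**4. NNAL.** Picograms per millilitre of creatinine is not a usable concentration unit. Plain picograms per millilitre is a cut-off without creatinine correction. A corrected and an uncorrected cut-off classify people differently, and the SAP does not say which is meant.

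**The case against.** The prose in 6.1 and 6.2 is right, and a careful programmer would see that '>5' exceeds a limit of 5. On that view Table 3 is only loose shorthand, and section 6.9 provides double programming. It is true that the intended up-to-5 definition can be recovered. But a second programmer working from the same table reproduces the same error. SAP section 7 (Table 4) also says that the study team, aware of allocation, took over all analyses, so an undocumented correction would be a choice made with allocation known.

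The two-of-three grace rule may have been meant to tolerate a missed call. That is plausible, but as written it equally tolerates a reported 'Yes', including at month 6.

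Part 3 depends on a form that is not shown. The row for change in cigarettes per day chains `quit_smoke_again` = Yes and then `quit_smoke_7days` = Yes, which may reflect skip logic. If the 7-day item is asked only after a 'Yes', the AND rule could pass nobody. The mismatch with 6.1 stands; its exact consequence does not.

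The month-6 anabasine, NNAL or CO check removes many current smokers from the validated rows. This stands. It does not remove people who smoked earlier and have since cleared the marker.

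**Conclusion.** Table 3 as written contradicts sections 6.1 and 6.2 for nine of the ten secondary abstinence outcomes. The tenth, continuous abstinence validated by NNAL, shares the unit problem. No other part of the SAP corrects this. In patterns, the size is 112 against 6 of 243 (up to 5), 4 against 1 of 8 (grace period) and 1 against 2 of 4 (7-day). These are counts of answer patterns, not of participants. Errors 1 and 2 act fully only in the self-report rows.

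A reader might infer more than the documents support:

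- *That the self-report up-to-5 rate would approach 80 to 100%.* Protocol Table 11.2-1 expects 111 + 340 = 451 of 586 (77%) and 17 + 473 = 490 of 586 (84%) still smoking at month 6. Nothing says how they would answer `quit_smoke_n`. The 29 per arm lost to follow-up count as smokers under SAP 6.5, so even the extreme is (586 − 29)/586 = 95%.
- *That the primary result is compromised.* Its self-report rule requires 'No' at weeks 1, 2, 4, 8 and month 6 and is untouched by these errors.
- *That the NNAL ambiguity means a tenfold spread in the cut-off.* That needs the per-milligram creatinine unit, which appears only in the superseded protocol 2.0, and an assumed creatinine range.

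**What to change.** - **Up to 5 cigarettes:** abstinent if there is no '>5' answer and no numeric daily-smoking record at any contact after the TQD, at most one '1-5' answer, and a completed month-6 report.
- **Grace period:** 'No' at month 6 and no 'Yes' at week 4 or week 8, with one stated rule for a missed call. Use the same self-report rule in the self-report and validated rows. First confirm from the eCRF that the item's recall period excludes the grace period; if it runs from the TQD, anyone who smoked in those two weeks would fail.
- **7-day point prevalence:** abstinent at month 6 if `quit_smoke_7days` is 'No', or if `quit_smoke_again` is 'No' where the 7-day item is skipped.
- **NNAL:** one cut-off in one valid unit throughout.

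Record these as dated SAP corrections; protocol section 11.4.6 already asks for deviations to be stated and justified. The cost is a look at the eCRF, rewording and recoding. No new data are needed.
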